2.1 Background & Aims

Yoga is an Indian mind-body practice that has become well-known all over the world. During standing, sitting, and lying supine or prone, participants' bodily motions are gradual and have a wide range of motion. It has been demonstrated that yoga practice improves balance, coordination, emotional and mental well-being which assist in increasing joint flexibility, range of motion (ROM) and muscle strength.

Three yoga poses namely; the crescent lunge pose (Halasana), warrior II pose (Virabhadrasana II), and triangle pose (Trikonasana). These yoga manoeuvres reduce pain, which enhances people's quality of life. Reports indicate that yoga alters the perception of pain and influences brain waves. Since yoga promotes both pain treatment and psychosocial healing, it has been a popular alternative pain management technique in recent years for Kinesio phobia.

Injured athletes can benefit from deep breathing as a non-pharmacological pain management technique that increases localized tissue circulation and diverts attention from their discomfort. Inducing a shift in sympathetic nervous system activity by reducing stress hormone levels and activating the diaphragm by stimulating the vagal nerve, which regulates pain perception, guided or focused deep breathing functions as a mindful meditation technique.

The most successful strategy for collegiate athletes to handle stress and prepare for competition was deep breathing. Additionally, it has been demonstrated that deep breathing can assist individuals with chronic musculoskeletal pain manage their condition effectively, reducing movement fear and enhancing subjective wellbeing and quality of life.

Conventional physical therapy includes exercises for strengthening and flexibility as well as training for agility and balance. These therapies aim to improve muscular strength, speed, agility, and neuromuscular control; restore a normal gait pattern without the use of assistive devices; improve balance; and increase range of motion and flexibility. Conventional physiotherapy uses a range of techniques centered on function restoration, strength enhancement, and injury prevention to address these problems.

By combining conventional physiotherapy with relaxation techniques like three typical yoga postures and deep breathing technique, our method not only helps people with Kinesio phobia but also improves their ankle range of motion, balance, and coordination so they can actively resume their daily lives.

2.2 Background Literature Review

YO Guvener et al (2023) pioneered the concept of 'psychological wellbeing through yoga poses': Regular meditation and yoga can enhance cognitive-emotional processes, which in turn can lead to greater psychological well-being. Yoga poses and breathing techniques have a significant impact on mental health. In a study by Deible et al., nurses who used stress reduction techniques like yoga and meditation reported feeling less stressed and having better coping skills.

Elizabeth Whissell et al (2021) proposed suggested that the motion patterns of the lunge and warrior II poses were comparable in terms of angular impulse, joint angles, and joint moments. Compared to the other two manoeuvres, the triangle position may be better since it increases hip joint range of motion, strength, and dynamic stability.

Bethany Forseth PhD et al (2021) suggests that practicing yoga has a connection to psychological well-being, as study participants who practiced yoga reported feeling less stressed and having fewer depressive symptoms than those who did not. Significant variations, however, were not found to substantiate the association between yoga practice and mitochondrial protein level and inflammatory indicators.

In a pilot study conducted by Ramalingam et al (2023) showed that young adults with Chronic Ankle Instability saw improvements in pain, balance, happiness, and attention after receiving Short-Duration Deep Breathing (SDDB) and Conventional Physiotherapy (CP) together for six weeks. In addition to the current Conventional physiotherapy, the gradual benefits of short duration deep breathing using smartphone applications among young adults as a pain management technique provide a further advantage to enhance the wellbeing of wounded sportsmen during their rehabilitation.

Bindu C.B et al. (2013) concluded that the immediate effects of deep breathing exercises on blood pressure, heart rate, and respiratory rate can be reversed very fast by just holding your breath until it breaks. This is likely due to central regulatory processes. On the other hand, peripheral variables that lower small airway resistance may provide a long-lasting, considerable 5% rise in peak respiratory flow rate. It implies that sympathetic dominance brought on by breath holding up to the breaking point swiftly counteracts the purported parasympathetic dominance brought on by deep breathing.

Volker Busch et al. (2012) pioneered Deep and slow breathing along with relaxation is the key component in the regulation of sympathetic arousal and pain perception since breathing patterns have a significant impact on autonomic and pain processing.

Laurel Long et al. (2013) pioneered the concept of '6-week at-home foot and ankle exercise' program was feasible and whether there would be any corresponding changes in older people' muscular function, flexibility, and balance. Participants showed statistically and clinically significant gains in the majority of the end measures after training. Further research is warranted since this study shows that a straightforward yet progressive home exercise program targeting the foot and ankle may improve several areas of balance and mobility in healthy older persons who live in the community.

3. Study Protocol

3.1 Research Design Outline

The study aims to perform a comparative study on chronic ankle instability with Kinesio phobia in Saveetha college of physiotherapy and Saveetha college of allied health sciences.

Formerly titled "Effectiveness of Three Typical Yoga poses and Conventional Physiotherapy for Kinesio phobia Among Football Players with Chronic Ankle Instability: A Comparative Study" involves amateur football players with Kinesio phobia by using the Tampa scale for Kinesio phobia and Cumberland ankle instability tool for Chronic ankle instability. The outcome is the total fear of movement, and fear of re-injury, severity of functional ankle instability. Total scores of 68 for Kinesio phobia, 30 for chronic ankle instability. Higher score means a better outcome.

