3.5 Assessment & Outcomes Measures

3.5.1 Primary outcomes

Tampa scale:

The Tampa scale will initially be used to distinguish between non-excessive fear and phobia in patients with chronic musculoskeletal pain, i.e., the fear of movement. In its original form, the TSK will be a 17-item assessment checklist. It will use a 4-point Likert scale (Strongly Disagree-Disagree-Agree-Strongly Agree) with statements that will later be linked to the model of fear-avoidance, fear of work-related activities, fear of movement, and fear of re-injury.

Cumberland ankle instability tool (CAIT):

The Cumberland Ankle Instability Tool (CAIT) will be a 9-item, 30-point scale that will measure the severity of functional ankle instability. Using a numeric value, the

Cumberland Ankle Instability Tool (CAIT) will have the ability to discriminate between stable and unstable ankles.

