4.1 Primary Outcomes

The primary analyses will compare experimental vs control group guidelines on their mean and standard deviation: (i)Tampa scale, (ii) Cumberland ankle instability tool (CAIT).

Comparison will be tested by using the Paired t test to find the significant difference within the intervention effects and between the two groups (Experimental control group and Experimental Group) using independent t-test. P values <0.05 has been considered statistically significant.

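### Section 3.1 says a higher score is better without excepting the Tampa scale, which measures fear of movement, and the SAP gives no direction to correct it

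*Combined protocol and SAP*

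**What the plan says.** Section 3.1 names the Tampa scale and the CAIT as the instruments and describes what they capture: "The outcome is the total fear of movement, and fear of re-injury, severity of functional ankle instability". It then gives the two totals and one statement of direction: "Total scores of 68 for Kinesio phobia, 30 for chronic ankle instability. Higher score means a better outcome".

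Section 3.5.1 lists both scales as primary outcomes. On Tampa it says: "The Tampa scale will initially be used to distinguish between non-excessive fear and phobia in patients with chronic musculoskeletal pain, i.e., the fear of movement". It gives 17 items on a four-category agreement scale, but no numeric codes and no reverse-scored items. The CAIT "will be a 9-item, 30-point scale that will measure the severity of functional ankle instability", and no direction is given there either.

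Section 2.1 indicates what counts as benefit. It credits deep breathing, one component of the programme, with "reducing movement fear and enhancing subjective wellbeing and quality of life", and says of the combined approach that "our method not only helps people with Kinesio phobia but also improves their ankle range of motion, balance, and coordination".

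Section 4.1 covers the analysis: "Comparison will be tested by using the Paired t test to find the significant difference within the intervention effects and between the two groups", with significance at P<0.05. Section 4.2 repeats this for the secondary outcomes. Neither says which direction is favourable or whether tests are one- or two-sided.

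**The concern.** A scale that totals fear, used in a trial meant to relieve fear, should improve by going down. The only direction rule in the documents says the opposite unless it is read as excluding Tampa, and its wording contains no such exclusion.

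Tampa is the first-listed of two primary outcomes. Someone who applied section 3.1 literally when reporting results would call a fall in fear a worsening and a rise an improvement. The SAP is where such a slip would normally be caught, but it asks only whether the groups differ.

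**Working it through.** **1. Does the stated total fit the scale described?** Inputs: 17 items and four response categories (section 3.5.1); total 68 (section 3.1).

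- Items coded 1 to 4: maximum 17 × 4 = 68, minimum 17 × 1 = 17.
- Items coded 0 to 3: maximum 17 × 3 = 51.

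The stated 68 is reproduced with 1–4 coding, which the documents do not state. This fixes the maximum only. It does not settle the direction.

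**2. What direction do the documents imply for Tampa?**

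| Place | Content | Implied direction |
|---|---|---|
| 3.1, outcome sentence | The outcome is an amount of fear | Higher = more fear |
| 3.5.1, Tampa | The scale separates ordinary fear from phobia | Higher = more fear |
| 2.1 | Helping kinesiophobia is what the method is for; less movement fear is a credited benefit | Less fear = better |
| 3.1, direction sentence | Higher is better, no exception | Higher = better |
| 4.1 and 4.2 | Test for a difference | None |

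The first three rows together give lower Tampa = better. The fourth contradicts them, and the fifth does not resolve it. No section describes a reversed total, which is what would be needed to reconcile them.

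**3. Do the other outcomes help?** Section 3.5.2 anchors the pain anxiety scale from 0 (none) to 100 (severe); 20 items × 5 = 100. Higher is therefore worse on that scale. This shows that the trial's outcomes do not all run the same way, but it says nothing about Tampa.

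**4. What changes if the direction is reversed?** With 1–4 coding, a reversed total is T′ = (17 + 68) − T = 85 − T. For group means m_E and m_C:

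- Difference: (85 − m_E) − (85 − m_C) = −(m_E − m_C). The size is the same and the sign is opposite.
- Standard deviations are unchanged, so t becomes −t.
- The two-sided p-value depends on |t| and is unchanged.
- A one-sided p-value becomes 1 minus itself. If fear falls with two-sided p = 0.05, the one-sided value is 0.05 / 2 = 0.025 when lower is better, and 1 − 0.025 = 0.975 when higher is better. This holds at any sample size.

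**The case against.** The strongest reply is that the direction sentence is singular and comes straight after the CAIT total, so it may refer to the CAIT alone. On that reading it says nothing false about Tampa. This is possible, and the text does not rule it out. But the first-listed primary outcome is then left with no direction at all, and the same edit is needed.

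A second reply is that no sentence says a higher Tampa total means more fear; this is inferred from the construct. The same inference applied to the CAIT, described as measuring severity of instability, would make a high CAIT score bad and contradict section 3.1 there too. This is a fair limit on arguing from the construct alone. The Tampa case is firmer because relieving kinesiophobia is plainly what the programme is for. For the CAIT, the direction sentence in 3.1 is all there is, so a reader who discards it for Tampa has nothing left for the CAIT.

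It can also be said that the movement-fear remark in section 2.1 is background on deep breathing rather than a trial objective. That is true; the statement about what the combined method does carries more weight.

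Finally, no computed result changes, no one-sided test is planned, and an analyst who sees the outcome named as fear is unlikely to report less of it as harm. All of this stands and limits the seriousness. It does not justify leaving the only direction rule contradictory for a primary outcome.

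**Conclusion.** The concern holds. As written, section 3.1 gives the wrong direction of benefit for Tampa; on the narrower reading it gives none. Nothing in the SAP repairs either case.

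The effect is on interpretation of one of two primary outcomes. Estimates and two-sided p-values are untouched; the benefit or harm label reverses. The change from 0.025 to 0.975 applies only if a one-sided test were used.

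The conclusion rests on taking a total described as fear to rise with fear, and on no reversed scoring being intended. Both follow from the documents' own wording. The 1–4 item coding is an assumption that matches the stated maximum, and the conclusion does not depend on it. This should be corrected, but it does not threaten the analysis itself.

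**What to change.** - **Section 3.1:** replace the single direction sentence with one statement per scale. Tampa (maximum 68): higher means more fear of movement and is worse; benefit is a reduction. CAIT (30 points): state its direction separately, consistent with the scoring form in use.
- **Section 3.5.1:** give the numeric coding of the Tampa items and name any that are reverse-scored.
- **Sections 4.1 and 4.2:** for each outcome, state which sign of the experimental-minus-control difference favours the experimental group, and state that tests are two-sided. The 3.1 correction is the essential one; for the secondary outcomes this is for completeness, since no direction error was found there.

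The cost is a wording amendment. It does not affect conduct, data collection or any computed result.

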3.2 Participants

Amateur football players from Saveetha Institute of Medical and Technical Sciences with Kinesio phobia along Chronic Ankle Instability will be eligible to participate in this study.

3.3 Recruitment

All amateur football players with Kinesio phobia along Chronic ankle instability attending Saveetha Institute of Medical and Technical sciences will be enrolled in the comparative study. The participation information and consent sheet will be distributed to amateur players which details including inclusion and exclusion criteria. Amateur players who agree to the investigation will be invited to undergo baseline assessments Tampa scale, Pain anxiety symptom scale, Y-balance test, Cumberland ankle instability tool (CAIT). All amateur players will have to return a signed consent form to the site principal investigator.

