4.3 Missing Data

For players who do not attend the assessment, the mean imputation of the assessment scores from their allocation group has been used.

5. Informed Consent Forms (ICF)

Written consent will be gained from the amateur football players with Kinesio phobia along with chronic ankle instability using the consent forms attached to the application.

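### The plan does not say how players are assigned to the two groups, and the unadjusted t-test gives no protection if the groups differ at baseline

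*Combined protocol and SAP*

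**What the plan says.** Section 3.1 labels the design only as a comparison: "The study aims to perform a comparative study on chronic ankle instability with Kinesio phobia". It places the study "in Saveetha college of physiotherapy and Saveetha college of allied health sciences".

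Section 3.3 enrols all eligible players: those "attending Saveetha Institute of Medical and Technical sciences will be enrolled in the comparative study". The next step is: "Amateur players who agree to the investigation will be invited to undergo baseline assessments". The baseline measures are the Tampa scale, the pain anxiety scale, the Y-balance test and the CAIT. Section 3.4 then describes yoga, deep breathing and conventional physiotherapy.

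Groups certainly exist, because section 4.3 handles missing scores this way: "the mean imputation of the assessment scores from their allocation group has been used". That is the only mention of allocation, and it does not say how the groups are formed.

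For the primary outcomes, section 4.1 makes the comparison "between the two groups (Experimental control group and Experimental Group) using independent t-test", with this threshold: "P values <0.05 has been considered statistically significant". Section 4.2 repeats the same test for the secondary outcomes. Neither section names a covariate, and neither says whether follow-up scores or changes from baseline are compared.

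**The concern.** An independent t-test estimates a treatment effect only if the two groups would have had the same expected outcome under the same treatment. Concealed random allocation secures that. Without it, covariate adjustment secures part of it, for what was measured. The written plan contains neither.

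All four outcome measures are taken at baseline, and no concealed step is described afterwards. The text therefore leaves open that known scores, or a player's liking for yoga, influence who joins which group. Fear of movement and pain anxiety could plausibly affect both that choice and the outcome. A gap that arises this way does not shrink as more players are recruited, and the test becomes more likely to call it significant.

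**Working it through.** **Search of the text.** Sections 3.1 to 4.3 run without a break, and an allocation procedure would be expected there. Read in order, they give: design label and colleges (3.1), eligible players (3.2), enrolment, consent and baseline tests (3.3), interventions (3.4), outcomes (3.5), analysis (4 to 4.2), missing data (4.3). None gives a sequence, ratio, concealment method, stratification or any other assignment rule. The word for randomised studies appears only in titles in the reference list.

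**Is there a figure to reproduce?** No. The plan states no sample size, power, effect size or SD, so the size of the problem can only be illustrated.

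**Assumptions (none from the documents except the 0.05 level):** no true treatment effect; systematic baseline gap g = 0.25 to 0.5 SD; pre-post correlation r = 0.5 to 0.7; equal SDs at both times; n = 20, 30 or 50 per group; two-sided test (the plan does not state sidedness). The gap is assumed to arise through the measured baseline score, so it carries forward as r × g.

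**Follow-up scores compared.**
- Bias in SD units: r × g, from 0.5 × 0.25 = 0.125 to 0.7 × 0.5 = 0.35.
- Noncentrality: r × g × √(n/2), with 2n − 2 degrees of freedom.
- Example, n = 20: 0.125 × √10 = 0.395 gives 6.7%; 0.35 × √10 = 1.107 gives 19.0%.

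**Changes compared.**
- The mean change differs by (1 − r) × g, and the SD of a change is √(2(1 − r)).
- Bias in SDs of change: g × √((1 − r)/2), from 0.25 × √0.15 = 0.097 to 0.5 × √0.25 = 0.25.
- Example, n = 20: 0.097 × √10 = 0.306 gives 6.0%; 0.25 × √10 = 0.791 gives 12.0%.

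| n per group | Follow-up scores | Changes |
|---|---|---|
| 20 | 6.7% to 19.0% | 6.0% to 12.0% |
| 30 | 7.6% to 26.6% | 6.6% to 15.9% |
| 50 | 9.5% to 41.0% | 7.7% to 23.6% |

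**Effect of adjustment.** A simulation (4,000 runs per setting; g = 0.5, r = 0.5 or 0.7, n = 20 or 30) gave false-positive rates of 12-26% for follow-up scores, 9-15% for changes and 4.9-5.4% for ANCOVA on the baseline score. ANCOVA does this well because the simulated gap acts only through the measured score. The result does not extend to unmeasured differences.

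**The case against.** **Silence is not evidence of non-random allocation.** A reader might infer that players are placed by choice or convenience. The documents do not say so, and the reference in 4.3 to an allocation group presupposes some process. Front matter and part of the consent section were not available for this review, and 3.1 gives only a former title, so a design label elsewhere cannot be excluded. This stands, and it limits the point to a method that is not described. A label alone would still not supply a sequence or concealment.

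**College.** Two colleges and two groups may suggest that each college forms one group, which would make treatment and college inseparable. No section links group to college, and 3.2 and 3.3 describe players of one institute. It is a question for the sponsor, not a finding.

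**Causal wording in 4.1.** It is tempting to read the sentence as attributing the between-group difference to the intervention. The phrase about intervention effects belongs to the paired, within-group test; the independent t-test is said only to compare the two groups. The concern does not need that reading. Nor does the paired test help, since it does not adjust the between-group comparison.

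**The illustration is conditional.** The gaps are assumed, and the rates are lower if changes are tested, which is why both columns are shown. The model also represents selection on a score that regresses towards the mean. A stable group difference would behave otherwise: it would carry over fully into follow-up scores (a 0.5 SD gap gives 34%, 48% and 70% with 20, 30 and 50 per group) and cancel in changes.

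**A non-randomised comparison is a legitimate design.** Agreed, provided that it is declared and the analysis and conclusion are fitted to it. The plan does neither.

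**Conclusion.** The point holds as an undescribed assignment method combined with an unadjusted between-group test. If assignment is in fact random and concealed, the t-test keeps its 5% level, and the defects are missing documentation and an analysis that ignores the baseline scores. If it is not, the plan has no safeguard. Under the stated assumptions the nominal 5% error then becomes 7-19%, 8-27% and 9-41% with 20, 30 and 50 per group for follow-up scores, or about 6-12%, 7-16% and 8-24% for changes. These figures show how the error behaves and are not estimates for this trial. The documents do not support the stronger statements that allocation is non-random or that it follows college. Confidence is medium, and the change should be made.

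**What to change.** 1. **Sections 4.1 and 4.2:** replace the unadjusted independent t-test with ANCOVA of the follow-up score on group and the baseline score of the same measure, which 3.3 already collects. Add college if players come from both colleges. This also settles whether scores or changes are analysed.
2. **Section 3.3, after baseline assessment:** add individual 1:1 allocation from a computer-generated list, concealed until the player is entered and held by someone who neither recruits nor assesses players. Stratify by college if both contribute. Section 5.2 says that an administration officer records the ID numbers. It does not say that this person assigns them or is independent of recruitment, so the sponsor should confirm that before giving the officer the list.
3. **If groups have been or will be formed non-randomly:** state this and the rule used in 3.1, and limit the conclusion to an association. Baseline adjustment does not remove unmeasured selection.
4. **Ask the sponsor** whether college is related to group.

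The cost is a paragraph of text, one list and a little more analysis work, with no extra players. The downside is that the site loses discretion over who receives which programme. If assignment has already been non-random, the claim the trial can make becomes weaker.
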